13.0 PHOTOGRAPHY

Standardized photographs will be taken of the treatment area. The subject will be asked to remove jewelry, make-up, and lotions prior to each photo session. Photographs will be taken with an appropriate high-resolution digital camera. Camera settings (lighting, distance, background, polarization, etc.) will be reproduced at each visit, so that photographs are suitable for comparison. Photographs will be taken of the treatment area for study purposes. If the subject does not wish to have their photographs taken, they cannot be in the study.

14.0 ADVERSE REACTIONS DEFINITIONS AND REPORTING REQUIREMENTS

All adverse events that occur, starting from the time of the first treatment, will be recorded in the source documents and Case Report Forms (CRF).

Adverse Events (AE) occurring will be captured and followed until the condition resolves, stabilizes, is otherwise explained, or the subject is lost to follow-up. Subjects will be instructed that they may contact the Investigator at any time throughout the course of the study.

The Investigator and/or designated study staff will review each event and assess its relationship to the study device (not related, unlikely, possible, probable, and highly probable). The following definitions will be used for rating relationship to the MyEllevate® procedure:

- Not related – The event is clearly related to other factors such as the subject's clinical state, therapeutic interventions, or concomitant medications administered to the subject.
- Unlikely – The event was most likely produced by other factors such as the subject's clinical state, therapeutic interventions, or a concomitant medication administered to the subject; and does not follow a known response pattern to the investigational product.
- Possible – The event follows a reasonable temporal sequence from the time of investigational product administration; **and/or** follows a known response pattern to the study sampling sessions; **but** could have been produced by other factors such as the subject's clinical state, therapeutic interventions, or concomitant medications administered to the subject.
- Probable – The event follows a reasonable temporal sequence from the time of investigational product administration; **and** follows a known response pattern to the investigational product; **and** cannot be reasonably explained by other factors such as the subject's clinical state, therapeutic interventions, or concomitant medications administered to the subject.
- Highly Probable – The event follows a reasonable temporal sequence from the time of investigational product administration; **and** follows a known response pattern to the investigational product; **and** cannot be reasonably explained by other factors such as the subject's clinical state, therapeutic interventions, or concomitant medications administered to the subject; **and** either occurs immediately following investigational product administration, **or** improves on stopping the investigational product, **or** reappears on repeat exposure, **or** there is a positive reaction at the application site.

Each adverse event reported will be graded on a 3-point severity. Using the following definitions for rating severity will be used:

- Mild – easily tolerated, causing minimal discomfort, and not interfering with normal everyday activities.
- Moderate – sufficiently discomforting and may interfere with normal everyday activities.
- Severe – incapacitating and/or preventing normal everyday activities.

A Serious Adverse Event (SAE) is any adverse device experience that results in any of the following outcomes: death, a life-threatening adverse device experience, in-patient hospitalization or prolongation of hospitalization, a persistent or significant disability/incapacity, or a congenital anomaly/birth defect. Important medical events that may or may not result in death, be life-threatening, or require hospitalization may be considered a serious adverse device experience when, based upon appropriate medical judgment, they may jeopardize the subject or subject may require medical or surgical intervention to prevent one of the outcomes listed in this definition

If any of the above adverse events are serious as defined by the FDA Code of Federal Regulations (CFR), Title 21, special procedures will be followed. All serious adverse events will be reported within 24 hours of acknowledgment to the Sponsor whether or not the serious events are deemed sampling session-related. All serious event reporting will adhere to 21 CFR part 812 and the IRB will be notified accordingly.

The SAE information will be entered into the database and a desk copy of the complete SAE report will be submitted to the study file.

Adverse events, whether serious or non-serious, will be followed until the condition is resolved, stabilized, otherwise explained or the subject is lost to follow-up. Adverse events will be captured throughout the study and where appropriate, medical tests and examinations will be performed to document the resolution of event(s). Outcomes may be classified as resolved, improved, unchanged, worse, fatal, unknown or lost to follow-up. Following the resolution of any study-associated adverse events there will be no further adverse event reports for that subject.

Reporting Adverse Events:

Report	Submit To	Description/Constraints
Adverse Events, Unanticipated Adverse Device Effect	IRB and Sponsor	If an unforeseen complication is determined to be an unanticipated adverse device effect, the investigator's report must be submitted within 10 working days after the investigator first learns of the effect.
Serious Adverse Events	IRB and Sponsor	The sponsor must be notified within 24 hours of serious adverse events. The IRB must be notified within 1 working day of serious adverse events as defined by FDA guidelines.

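### The causality scale has no valid rating for an event with plausible timing, no other explanation and no known response pattern, and it bars such an event from the two highest levels

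*Combined protocol and SAP*

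**What the plan says.** Section 14.0 asks the investigator or designated staff to rate the relationship of each event to the device as one of "not related, unlikely, possible, probable, and highly probable". There is no unclassifiable level and no rule for an event that fits no definition.

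- **Not related:** the event is clearly due to other factors.
- **Unlikely:** other factors most likely produced it, and it does not follow a known pattern.
- **Possible:** timing is reasonable and/or the event "follows a known response pattern to the study sampling sessions"; but it "could have been produced by other factors such as the" subject's condition or other treatment.
- **Probable:** three conditions joined by *and*. The first is timing ("The event follows a reasonable temporal sequence from the time of investigational product administration"), the second is that the event "follows a known response pattern to the investigational product", and the third is that it "cannot be reasonably explained by other factors".
- **Highly Probable:** the same three conditions, plus one of four alternatives: immediate onset, "improves on stopping the investigational product", recurrence on repeat exposure, or a positive reaction at the application site.

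Section 1.2 makes the collection of adverse events the primary objective. Section 3.2 tells the reader that some side effects may not yet be known.

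**The concern.** A study run because the safety profile is uncertain (section 3.3) should be able to say that a new kind of event was probably caused by the procedure. Here, prior knowledge of the effect is a condition for saying so. The phrase known response pattern is not defined, and the possible benchmarks differ. Section 2.14 lists expected and possible effects, section 3.2 equates the risks with those of non-ablative radiofrequency treatment, and section 4.0 describes a suture system.

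With two centres and more than one possible rater, the same unmatched event could receive different labels. Success under section 2.15.1 is a side effect profile that the physician finds acceptable, with no numerical criterion, so recorded causality could well feed that judgement.

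**Working it through.** The plan states no figure to reproduce here. The check is logical: test the event against each definition, then enumerate the combinations.

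**Step 1. The event at issue.** Timing reasonable: yes. Known pattern: no. Other cause: cannot reasonably explain it.

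| Level | Condition that fails | Conditions failed |
|---|---|---|
| Not related | clearly due to other factors | 1 |
| Unlikely | most likely due to other factors | 1 |
| Possible | other factors could have produced it | 1 |
| Probable | known pattern | 1 |
| Highly Probable | known pattern (and the extra criterion, if not met) | 1 or 2 |

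No level fits. Counting failed conditions does not point to a nearest level either, because the first four levels each fail exactly one.

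**Step 2. All combinations.** Timing (yes/no) × known pattern (yes/no) × other cause (clearly, most likely, could be, cannot reasonably be) gives 2 × 2 × 4 = 16 cells. A cause that is most likely is taken to satisfy Possible's requirement that it could have produced the event. Four cells have no category:

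1. timing yes, pattern no, cannot be other;
2. timing no, pattern yes, cannot be other;
3. timing no, pattern no, could be other;
4. timing no, pattern no, cannot be other.

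Only the first has plausible timing. If a most likely other cause were held not to satisfy Possible, the two known-pattern cells with that cause would also be empty, giving 4 + 2 = 6. The first cell is empty on either reading.

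**Step 3. Effect of removing known pattern as a condition for Probable.** Cell 1 becomes Probable. Under the main coding, all eight cells with plausible timing then have at least one category. The three cells without plausible timing stay empty.

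**Step 4. Context for 10 subjects.** Section 2.15.2 plans 10 subjects. The chance of at least one subject with an event of true rate p is 1 − (1 − p)^10. The rates below are assumed, since the documents give none.

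- p = 5%: 1 − 0.95^10 = 40%; expected subjects 10 × 0.05 = 0.5
- p = 10%: 1 − 0.90^10 = 65%; expected subjects 10 × 0.10 = 1
- p = 20%: 1 − 0.80^10 = 89%; expected subjects 10 × 0.20 = 2

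A new effect may well be seen only once, so the rating of a single event can matter.

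**The case against.** The strongest reply is that the event is not lost. Section 14.0 records all events from the first treatment. Section 2.14 has the sponsor or a designee review every documented event for regulatory reporting. Section 2.15.6 summarises numbers and percents of patients without restricting them to related events. Serious events go to the sponsor whether or not they are judged related. All of this stands, and it confines the defect to the causality label. None of it supplies a valid rating for a non-serious new event.

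A second reply is that section 2.14 lists so many effects that few events would lack a known pattern. That may make the cell narrow, but the plan does not say that this list is the benchmark, and section 3.2 allows for effects outside it.

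Four stronger readings are tempting, and the documents do not support them:

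- **That new events are forced down to Possible or Unlikely.** Both levels need another cause, which this event lacks. Strictly it cannot be rated. A rater who must choose and enforces the known-pattern condition can go no higher than Possible, but only by ignoring Possible's own condition. One who waives the known-pattern condition could choose Probable.
- **That reporting of unanticipated effects depends on the rating.** The reporting table says only "If an unforeseen complication is determined to be an unanticipated adverse device effect", and ties that determination to no level of the scale.
- **That a rate of probable-or-higher events would be biased by a stated amount.** No such rate is planned.
- **That the stopping and repeat-exposure criteria block Highly Probable.** They fit poorly with a single device use (section 2.12) and a nonabsorbable suture (section 4.0), but they are alternatives joined by *or*. Immediate onset or a reaction at the site is enough.

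The sampling-session wording in Possible is also of limited effect, because timing alone satisfies that part of the definition.

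**Conclusion.** The gap is real and follows from the text alone. An event with reasonable timing, no other reasonable explanation and no known pattern fits 0 of 5 levels, and any event without a known pattern is barred from the top two. This is a stated rule that yields no valid answer, not a missing detail.

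Its reach is the recorded causality and any safety judgement that draws on it, not the adverse event counts or the reporting of serious events. The conclusion assumes that the definitions are applied as written. How often such an event will occur in 10 subjects cannot be derived from the documents. The point should be corrected because safety is the primary objective and the edit is small.

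**What to change.** In section 14.0, and in any case report form text that repeats it:

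1. Define Probable by its timing condition and its no-other-reasonable-explanation condition, and add that it applies whether or not the event follows a known response pattern.
2. Known pattern may stay as a condition for Highly Probable, where it usefully separates the top two levels. A new effect could then reach Probable but not Highly Probable.
3. Replace the sampling-session wording, both in Possible and in the paragraph on reporting serious events, with a reference to the MyEllevate procedure and to procedure-related events.
4. Optional tidying: delete the stopping and repeat-exposure alternatives, and add one sentence on how to rate an event that fits no definition, which would cover the three cells without plausible timing.

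The cost is a wording amendment with IRB approval, as section 21.0 requires. Visits, sample size and treatment do not change. The downside is that a few more events may be rated as related, which is the cautious direction for a safety study.

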15.0 PROTOCOL DEVIATIONS

All requests for protocol deviations by the Investigator must be communicated to the sponsor in writing and if accepted by the Sponsor must be approved by the IRB. If a deviation occurs, the Investigator must inform the Sponsor as soon as possible. The Sponsor will notify the IRB in accordance with IRB specific policies.

16.0 CONFIDENTIALITY AND DISCLOSURE OF MEDICAL INFORMATION

As part of this study the Investigator and the team at the research facility will keep records of subject participation in the study. These study records will include personal information that the subjects provide including age, sex, etc., the results of the study, information about response to treatments, photographs taken during the study and other medical information relating to participation in the study.

Under federal law the study records cannot be used or disclosed by the Investigator for research purposes unless subjects sign the informed consent authorization.

Some or all of the test results, photographs and other information will be reported to Cynosure, LLC, the manufacturer of the test device (Sponsor), and consultants that are helping conduct the study. The Sponsor and its consultants will analyze and evaluate these results and information and may report them to the U.S. Food Administration and the FDA, Institutional Review Board or other regulatory agencies in the United States and/or foreign countries. The subject's study records will be assigned a code number by the study team and they will ordinarily not be identified by name in

the study records that are sent to the Sponsor and its consultants. However, The Sponsor, the Institutional Review Board and its consultants will have the right to see the complete study records, including the subject's name, and might choose to do so. If reports or articles are written about the study, the subject will not be identified by name in them however your study information and photographs may be used.

The research facility will review and use the study records only for purposes of this study. They will keep the subject's identity confidential and, except for the disclosures described above, will not disclose the study records to other parties unless disclosure is required by law. Once the research facility discloses information in the study records, photographs or medical records to the Sponsor or its consultants, the information will no longer be protected by federal law. Because of the need to release information to these parties, absolute confidentiality cannot be guaranteed. However, the Sponsor and its consultants will only use information for purposes of the study and will not disclose your study records to parties other than; the FDA or other regulatory agencies in the United States and/or foreign countries, unless disclosure is required by law. If reports or articles are written about the study, subjects will not be identified by name in them however, subject study information and photographs may be used.

Study records will be kept at the research facility according to applicable regulations and policies and may be kept indefinitely following the completion of the study. Subjects will not have the right to review their records while the research is in progress. However, they will be able to review their records after the research has been completed.

17.0 CLINICAL RESEARCH CONDUCT

The study will be conducted in accordance with the protocol, International Conference on Harmonization (ICH) GCP guidelines, applicable regulations and guidelines governing clinical study conduct and ethical principles that have their origin in the Declaration of Helsinki. The investigator must ensure that the study is conducted in accordance with the provisions as stated in the FDA regulations and complies with the applicable local or regional regulatory requirements.

18.0 REPORTING FOR THE STUDY

A study summary report will be generated. It will include a description of the clinical conduct of the study and results.

Study Summary Reporting:

Report	Submit To	Description/Constraints
Deviation from Investigational Plan	IRB and Sponsor	A deviation performed in an emergency to protect the life or physical well-being of a patient necessitates notification of the IRB and sponsor. The Investigator's report must be submitted within 5 working days after the emergency occurred. Deviations in a non-emergency situation require notification to sponsor prior to implementation

Failure to Obtain Informed Consent	IRB and Sponsor	The Investigator must make notification within 5 working days after device use, using the Protocol Deviation CRF. The report must include a brief description of the circumstances justifying the failure to obtain informed consent.
Final Report	IRB and Sponsor	The Investigator must submit a final report within 3 months after termination or completion of the investigation.
Withdrawal of IRB approval	Sponsor	The Investigator must report a withdrawal of the reviewing IRB approval within 5 working days .
Progress Report	IRB, Monitor and Sponsor	The Investigator must submit progress reports at regular intervals, and as required by the IRB, but in no event less than annually.

19.0 DISCLOSURE

The Principal Investigator and Cynosure employees and consultants have signed confidentiality agreements with the sponsor. This confidentiality agreement ensures that all information provided to the Investigator or Data Management and Statistics group dealing with the study and information obtained during the study will be regarded as confidential.

20.0 RESPONSIBILITY OF THE INVESTIGATOR

The Investigator is responsible for ensuring that the clinical study is performed in accordance with the International Conference on Harmonization (ICH), Good Clinical Practice (GCP) guidance E6, FDA Good Clinical Practice Regulations, Declaration of Helsinki (DoH) and the Health Human Service (HHS) Belmont Study. Investigators will supply information to the sponsor such that the sponsor can comply with the Financial Disclosure Rules.

21.0 PROCEDURE FOR AMMENDMENTS TO PROTOCOL

No deviations from this protocol will be permitted, except in a medical emergency, without the approval of the Sponsor. Any amendment to this study will be discussed by the Investigator and the Sponsor. If agreement is reached concerning the need for modification, this will be made in a formal amendment to the protocol.

All revisions and/or amendments to the protocol must be approved in writing by the appropriate Institutional Review Board.

22.0 TERMINATION OF STUDY

The Sponsor reserves the right to discontinue this study for administrative reasons at any time. The Investigator reserves the right to discontinue the study for safety reasons at any time in collaboration with the Sponsor.

23.0 DATA SECURITY

To ensure the privacy and confidentiality of data for this protocol, the data will be stored on a restricted access location on a company server. Access to the project directory containing the data will be limited to the Investigators and research staff. Information about data security awareness is promoted through user training and education, supplemented by policies and procedures. Password protection will be used for all transactions that allow viewing, editing, and analysis of data, or that provide access to data fields derived from the original source documents.

24.0 REPORT OF PRIOR INVESTIGATIONS

The report of prior investigations or predicates are:

Device	Determination	510(k)
Featherlift Extended Length Aptos Threads (Contour Threads)	Meets the criteria for exemption from IDE regulations, non-significant risk	K041593
FaceTite™	Meets the criteria for exemption from IDE regulations, non-significant risk	K151793

Protocol	Device	IRB Name	Determination	Initial IRB Approval Date
7053-RETRO-2022	MyEllevate®	AIRB	Meets the criteria for exemption from IDE regulations, non-significant risk	3/3/2022

[figure not shown]
APPENDIX A: Protocol Revisions Tracker

Version Date	Editor	Description
June 5, 2022	[name]	IRB Submission
June 14, 2022	[name]	IRB Response

